4.6 TREATMENT, PATIENT, STUDY, AND SITE DISCONTINUATION

4.6.1 Study Treatment Discontinuation

Patients must permanently discontinue study treatment if they experience any of the following:

- Any medical condition that the investigator or Sponsor determines may jeopardize the patient's safety if he or she continues to receive study treatment
- Investigator or Sponsor determination that treatment discontinuation is in the best interest of the patient
- Pregnancy
- Meet the discontinuation criterion in the risk mitigation strategy (see Section 5.1).
- Continuation of treatment should be carefully assessed in case of multiple or severe relapses that are not in keeping with the patients NMOSD history or trajectory.

The investigator should consult with the Medical Monitor if these relapses meet this criterion.

- Malignancy or a severe allergic or anaphylactic reaction to satralizumab.

The primary reason for study treatment discontinuation should be documented on the appropriate eCRF page. Patients who discontinue study treatment will not be replaced.

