1.2 BACKGROUND ON SATRALIZUMAB

Satralizumab (RO5333787; ENSPRYNG®) is a humanized anti-human IL-6R blocking monoclonal antibody that was designed by application of recycling antibody technology.

Antibody engineering techniques were utilized to give satralizumab pH-dependent binding affinity to IL-6R so that it binds to IL-6R under neutral conditions in plasma but dissociates under the slightly acidic conditions in endosomes, and is recycled to the plasma instead of being degraded in lysosomes, resulting in a longer plasma half-life. In addition, satralizumab is a modified IgG2 isotype, which reduces Fc-mediated effector functions.

The Clinical Development Program of satralizumab in NMOSD currently consists of two ongoing pivotal placebo-controlled, randomized, double-blind Phase III studies: Study BN40898 in adult and adolescent patients treated with 120 mg subcutaneous (SC) satralizumab in addition to background immunosuppressive therapy (IST) and Study BN40900 in adult patients treated with 120 mg SC satralizumab as a monotherapy. Both studies are ongoing in their open-label extension (OLE) periods.

Data from the completed double-blind periods of the pivotal Phase III Studies BN40898 (Yamamura et al. 2019) and BN40900 (Traboulsee et al. 2020) in adult and adolescents with NMOSD demonstrated a substantial magnitude of clinical benefit. Treatment with satralizumab led to significant reductions in the risk of protocol-defined relapse of 62% in

Study BN40898 (hazard ratio [HR]=0.38; 95% CI: 0.16 to 0.88) and 55% in Study BN40900 (HR=0.45; 95% CI: 0.23 to 0.89) compared with placebo.

Benefit was evident across multiple subgroups and was particularly high in the subgroup of patients who were AQP4-IgG seropositive, with risk reductions of 79% (HR=0.21; 95% CI: 0.058 to 0.750; p=0.0086) and 74% (HR=0.26; 95% CI: 0.108 to 0.627; p=0.0014) in Studies BN40898 and BN40900, respectively. Evidence of benefit in the subgroup of patients who were AQP4-IgG seronegative was inconclusive.

Based on the results of the studies summarized above, satralizumab (ENSPRYNG) has been approved by multiple Health Authorities as monotherapy or in combination with IST for the treatment of NMOSD in adult and adolescent patients who are anti-AQP4 seropositive, and is currently under review by other Health Authorities worldwide.

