3. STUDY DESIGN

3.1 DESCRIPTION OF THE STUDY

3.1.1 Overview of Study Design

This Phase IIIb study is a multicenter, single-arm, open-label study for approximately 127 patients who completed the OLE period of Study BN40898 and Study BN40900, (i.e., were receiving ongoing treatment with satralizumab prior to study entry in this Study WN42349). The study aims to evaluate the long-term safety and efficacy of satralizumab in patients with NMOSD.

Informed consent should be obtained from participants while they are in the parent Studies BN40898 or BN40900. Patients will be transitioned from their ongoing Study BN40898 or BN40900 at a planned dosing visit to allow for continuous dosing with SC satralizumab at a dose of 120 mg (fixed dose) every 4 weeks (Q4W). Safety and efficacy will be assessed at the baseline visit in this study. Efforts will be made to transition patients, at a 12-week or 24-week visit in their visit schedule in the parent study to reduce burden of assessments on patients.

[figure not shown]
Patients will receive satralizumab as monotherapy or in combination with one of the following background immunosuppressive treatments: AZA, MMF, or oral corticosteroids. Patients aged less than 18 years at the time of informed consent for Study BN40898 can continue treatment with a combination of oral corticosteroids and either AZA or MMF. It is at the discretion of the investigator to modify the background treatment after the baseline visit in this study (see Section 4.4.1). For patients who experience a relapse during the study, appropriate acute relapse/rescue therapy will be initiated.

The treatment period with satralizumab will be 3 years from the date the first patient enrolls in this study. Patients who withdraw from treatment will be asked to complete an End of Treatment visit followed by a Safety Follow Up (SFU) period of 12 weeks from the last dose of study drug prior to the End of Study visit (see Section 4.6).

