4.3.2 Dosage, Administration, and Compliance

Satralizumab 120 mg will be administered by SC injection in the abdominal or femoral region by the Investigator or designated person after all other study-related procedures have been performed at a site visit.

Patients will receive an SC injection of satralizumab at the baseline visit and every Q4W thereafter, with the last study drug administration on or before the date 3 years after the first patient was enrolled.

Patients who experience a relapse during the study will continue administration of satralizumab at the discretion of the investigator.

In accordance with local regulations, administration of satralizumab prefilled syringes outside of the study site (e.g., self-administration or administration by a caregiver after completing training) may be allowed on scheduled study drug administration days that do not require additional assessments that must be performed on site ([Appendix 1](#)).

If study drug cannot be administered within the scheduled visit window and is subsequently administered outside the visit window, the next dose of study drug should be administered on schedule (minimum dosing interval should be 14 days).

The treatment regimen is summarized in Section [3.1](#).

See the pharmacy manual for detailed instructions on study drug storage and administration.

Details on treatment administration (e.g., dose and timing) should be noted on the Study Drug Administration electronic Case Report Form (eCRF). Cases of overdose, medication error, drug abuse, or drug misuse, along with any associated adverse events, should be reported as described in Section [5.3.5.12](#).

Guidelines for treatment interruption or discontinuation for patients who experience adverse events are provided in Section 5.1.

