4.5.14 Assessments at the Treatment Discontinuation and End of Study Visit

The treatment discontinuation (EOT) visit is for patients who discontinue from satralizumab treatment in this study. At this visit, a complete set of assessments will be conducted. If the EOT coincides with a scheduled visit, the EOT visit should be completed instead of the scheduled visit. Patients will be asked to attend an End of

Study (EOS) visit 12 weeks after the last dose of satralizumab to complete the SFU period.

Patients who decide to continue treatment with satralizumab outside of this study have to complete the EOT visit, but they will not have to complete the SFU.

After the final study visit, AEs should be reported and followed as outlined in Section 5.5 and Section 5.6.

See [Appendix 1](#) for the schedule of activities performed at the EOT and EOS visits.

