5.1.2.2 Malignancies

Although malignancies have been reported in patients given other IL-6R antibodies, there have been no reports to date that there is an appreciably increase in the occurrence of malignancies. No increased risk of malignancies has been observed in clinical trials with satralizumab treatment.

Satralizumab should be discontinued in patients with malignancies (with the exception of local basal or squamous cell carcinoma of the skin that is completely excised with free margins).

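### Section 4.6.1 makes any malignancy a mandatory permanent stop, while Section 5.1.2.2 exempts fully excised local basal or squamous cell skin cancer, and nothing says which rule governs.

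*Combined protocol and SAP*

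**What the plan says.** Section 4.6.1 opens with a mandatory, permanent instruction that applies when any one item in its list is met. One item reads "Malignancy or a severe allergic or anaphylactic reaction to satralizumab". It has no exception and does not refer to Section 5.1.2.2. Another item in the same list reads "Meet the discontinuation criterion in the risk mitigation strategy (see Section 5.1").

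Section 5.1.2.2 deals specifically with malignancy. It says satralizumab should be discontinued, "with the exception of local basal or squamous cell carcinoma of the skin that is completely excised with free margins".

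Section 4.3.2 tells sites: "Guidelines for treatment interruption or discontinuation for patients who experience adverse events are provided in Section 5.1".

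Three further provisions determine what a stop costs:

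- Dosing runs every 4 weeks, "with the last study drug administration on or before the date 3 years after the first patient was enrolled" (Section 4.3.2).
- A patient who stops has an end-of-treatment visit, "followed by a Safety Follow Up (SFU) period of 12 weeks from the last dose of study drug" (Section 3.1.1).
- Section 4.5.14 adds "Patients who decide to continue treatment with satralizumab outside of this study have to complete the EOT visit", and excuses those patients from the safety follow-up.

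**The concern.** The protocol sends an investigator to two places for the same decision, and the two places differ for one identifiable kind of patient. Someone with a small, fully excised basal cell carcinoma must stop permanently under Section 4.6.1. Section 5.1.2.2 takes the same patient out of its advice to stop.

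The stakes for the patient are an unintended end to in-study relapse prevention, in a disease where Section 1.1.1 says relapses often leave irreversible deficits. For the study, they are lost long-term exposure and inconsistent handling across about 56 sites (Section 9.5). Withdrawals due to adverse events are a named safety variable in Section 6.6, so differing readings would pass into that table. Section 9.2 does not allow prospective requests to deviate. A site that follows Section 5.1.2.2 could therefore be recorded as deviating from Section 4.6.1, with no waiver available.

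**Working it through.** The plan gives no figure on this point to reproduce. The check is a comparison of texts, followed by simple arithmetic on the protocol's durations.

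**Texts side by side, for a fully excised local basal or squamous cell skin carcinoma**

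| Place | Does this patient have to stop? |
|---|---|
| 4.6.1, malignancy item | Yes, permanently; no exception |
| 5.1.2.2 | No; exempt from the advice to stop |
| 4.6.1, item pointing to 5.1 | Not triggered, but does not cancel the malignancy item |
| 4.3.2, pointer to 5.1 | Sends sites to the exemption; sets no order of precedence |

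The third row decides the matter. The Section 4.6.1 list operates when any single item is met. Failing to meet the Section 5.1 item therefore leaves the separate malignancy item in force. That pointer can add reasons to stop but cannot remove one.

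**What a literal stop costs one patient**

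Inputs:

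- Treatment ends 3 years after the first patient enrols (Section 4.3.2), taken as 3 × 52 = 156 weeks.
- Dosing is every 4 weeks (Section 4.3.2).
- Safety follow-up lasts 12 weeks from the last dose (Section 3.1.1).
- The week *t* of the last dose is an assumption. The documents give no event rate.

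For the first-enrolled patient, with safety follow-up completed in both scenarios:

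- Follow-up ends at week *t* + 12 instead of 156 + 12 = 168.
- Follow-up lost = 168 − (*t* + 12) = 156 − *t* weeks.
- Study doses lost = (156 − *t*)/4.

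| Last dose *t* | Follow-up ends | Instead of | Weeks lost | Study doses lost |
|---|---|---|---|---|
| 52 | 64 | 168 | 104 | 104/4 = 26 |
| 104 | 116 | 168 | 52 | 52/4 = 13 |

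The end of treatment is a calendar date tied to the first enrolment. A patient enrolled *e* weeks later, with *t* counted from that patient's own baseline, loses 156 − *e* − *t* weeks. The table is therefore the maximum for each *t*.

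**Sensitivity to the waiver of safety follow-up**

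Patients who continue satralizumab outside the study finish at the end-of-treatment visit, taken here to fall at about the last dose. For *t* = 52:

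- The stopper completes follow-up, and would otherwise have finished treatment and continued outside: 156 − 64 = 92 weeks lost.
- The stopper continues outside, and would otherwise have completed follow-up: 168 − 52 = 116 weeks lost.
- Both routes are outside: 156 − 52 = 104 weeks lost.

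The range is 92 to 116 weeks. The count of 26 study doses is the same in each case.

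**The case against.** The strongest reply is that ordinary reading settles the matter. Section 5.1.2.2 is the only section devoted to malignancy and is the more specific rule. Section 4.3.2 sends sites to Section 5.1. The Section 4.6.1 list is also loosely drafted: its relapse item asks only for careful assessment, despite the mandatory opening. This makes the intended meaning fairly clear, but it does not supply a rule of precedence. The relapse item carries its own softer wording and the malignancy item has none. The stricter verb is in Section 4.6.1, so a cautious site or monitor could reasonably enforce it.

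A second point is that the exception only lifts the advice to stop; it does not order treatment to continue. That is correct. A site that stops such a patient breaches nothing in Section 5.1.2.2. The conflict is over whether the patient must stop, and on that the two sections differ.

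Third, the stop weeks are arbitrary and the first-enrolled patient is the extreme case. This also stands: the figures show the scale per affected patient and are not an expected loss. The lost doses are study doses, and the patient may obtain the drug elsewhere.

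Fourth, follow-up of the malignancy does not simply end. Section 5.5.1 requires each adverse event to be followed to resolution or stability, and Section 5.6 keeps drug-related serious events notifiable after the reporting period. What stops is scheduled efficacy assessment and, 3 months after the last dose, general adverse event collection (Section 5.3.1).

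Finally, the ITT and safety populations keep these patients (Sections 6.1.1 and 6.1.3), and the safety analyses are descriptive. That limits the effect on analysis but does not correct the stopping instruction.

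**Conclusion.** The concern holds. For a patient with a fully excised local basal or squamous cell skin cancer, Section 4.6.1 as written requires a permanent stop that Section 5.1.2.2 does not, and no text in the protocol resolves the difference.

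The size is modest. Probably very few patients would be affected, and the documents give no basis for a count. Per affected first-enrolled patient, the loss is 26 study doses and 104 weeks of follow-up for a last dose at week 52, or 13 doses and 52 weeks at week 104. This assumes 156 weeks of treatment and completed safety follow-up either way.

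Harm is limited because satralizumab "has been approved by multiple Health Authorities as monotherapy or in combination with IST" for AQP4-seropositive adults and adolescents (Section 1.2). That protection is incomplete. Seronegative patients may enrol (Section 4.1.1), and the sponsor's continued-access offer is framed for patients who have completed the study (Section 4.3.4). No sample size, power or error rate is affected. The text should be corrected because it is an operative stopping rule.

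**What to change.** In the Section 4.6.1 item, place a parenthesis directly after the word malignancy that repeats the exception, "with the exception of local basal or squamous cell carcinoma of the skin that is completely excised with free margins", and refers to Section 5.1.2.2. Leave the rest of the item, on allergic and anaphylactic reactions, unchanged. The investigator or sponsor can still stop such a patient under the first two items of the list, so no safety discretion is lost.

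The cost is a protocol amendment. Section 9.7 requires ethics approval, and regulatory approval where local rules demand it, before the change takes effect at the roughly 56 sites. It can be bundled with the next amendment and adds no visit, patient or analysis.

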4.6.2 Patient Discontinuation from the Study

Patients have the right to voluntarily withdraw from the study at any time for any reason. In addition, the investigator has the right to withdraw a patient from the study at any time.

Reasons for patient discontinuation from the study may include, but are not limited to, the following:

- Patient withdrawal of consent
- Study termination or site closure
- Adverse event
- Loss to follow-up

- Patient non-compliance, defined as failure to comply with protocol requirements as determined by the investigator or Sponsor

Every effort should be made to obtain a reason for patient discontinuation from the study. The primary reason for discontinuation from the study should be documented on the appropriate eCRF. If a patient requests to be withdrawn from the study, this request must be documented in the source documents and signed by the investigator. Patients who withdraw from the study will not be replaced.

When participants complete the treatment period or discontinue early, every effort should be made to ensure that the safety follow-up period and all related assessments are completed. Patients will return to the clinic for a study discontinuation/EOS visit 12 weeks after the final dose of satralizumab.

4.6.3 Study Discontinuation

The Sponsor has the right to terminate this study at any time. Reasons for terminating the study may include, but are not limited to, the following:

- The incidence or severity of AEs in this or other studies indicates a potential health hazard to patients
- Patient enrollment is unsatisfactory

The Sponsor will notify the investigator if the Sponsor decides to discontinue the study.

4.6.4 Site Discontinuation

The Sponsor has the right to close a site at any time. Reasons for closing a site may include, but are not limited to, the following:

- Poor protocol adherence
- Inaccurate or incomplete data recording
- Non-compliance with the International Council for Harmonisation (ICH) guideline for Good Clinical Practice
- No study activity (i.e., all patients have completed the study and all obligations have been fulfilled)

5. ASSESSMENT OF SAFETY

5.1 SAFETY PLAN

The safety plan for patients in this study is based on clinical experience with satralizumab in completed and ongoing studies, as well as experience with molecules in the same class. The anticipated safety risks for satralizumab are outlined below. See the current satralizumab Investigator's Brochure for a complete summary of safety information.

Several measures will be taken to ensure the safety of patients participating in this study. Patients will undergo safety monitoring during the study, including assessment of the nature, frequency, and severity of AEs. The safety risks for satralizumab or anti-IL-6R antibodies and recommendations for vigilance with signs and symptoms of particular safety events are summarized in the following sections.

5.1.1 Risks or Laboratory Abnormalities Associated with Satralizumab

5.1.1.1 Infections

Treatment with IL-6R inhibitors suppresses acute phase reactions (fever, increase in CRP, etc.) induced by IL-6 and accordingly suppresses signs and symptoms associated with infection, which may delay the detection of infections and they may become more severe as a result of initial masking. In the double-blind period of Phase III Studies BN40909 and BN40900, the rates of overall infections and serious infections in patients treated with satralizumab monotherapy or in combination with IST were not higher than the placebo groups.

Management of Infections and serious infections:

- Patients should be closely monitored for the development of signs and symptoms of infection, because signs and symptoms of acute inflammation may be lessened as a result of suppression of the acute phase reactants.
- Patients must be instructed to contact their physician immediately when any symptoms suggesting infection appear, in order to ensure rapid evaluation and appropriate treatment.
- The administration of satralizumab should be delayed until the active infection is controlled.
- If a patient develops a serious infection, administration of satralizumab is to be interrupted until the infection is resolved. The treating physician should conduct a benefit-risk assessment before resuming treatment with satralizumab.
- Live or live attenuated vaccines should not to be given during the course of the study as clinical safety has not been established.

For patients with NMOSD participating in this study, therapies used to treat NMOSD (i.e., corticosteroids, AZA, MMF) have been shown to be associated with infections, particularly serious infections.

5.1.1.2 Serious Hypersensitivity Reactions

Anaphylaxis and hypersensitivity reactions are considered a potential risk for all biologic medications, including satralizumab. As of February 2020, no anaphylaxis or serious hypersensitivity reactions have been reported in clinical trials with satralizumab.

The symptoms/signs of hypersensitivity include, but are not limited to, blood pressure decrease, dyspnea, loss of consciousness, dizziness, queasiness, vomiting, itchiness,

flushing, etc. A decision to continue/discontinue treatment with satralizumab should be made taking into account the risks and benefits if any of these events are observed:

- If an anaphylactic reaction or other serious hypersensitivity reaction occurs, satralizumab should be discontinued. At the study site, the SC injections should be administered under close supervision in a setting where medications (e.g., corticosteroid, antihistamine, and epinephrine) and resuscitation facilities are available
- Patients should be instructed to seek medical attention if they experience symptoms of hypersensitivity reaction outside of the clinic.
- Administration of satralizumab prefilled syringes outside of the study site might be allowed (see Section 4.3.2) if the investigator determines that it is appropriate. Patients/caregivers should be instructed to recognize the signs and symptoms of hypersensitivity reactions and instructed to seek immediate medical attention if the patient develops symptoms of serious allergic reactions. Patients/caregivers should confirm with the investigator whether treatment with satralizumab may be continued.

5.1.1.3 Liver Enzyme Elevations and Potential Risk of Hepatotoxicity

It has been reported that IL-6 appears to have a hepato-protective effect on various forms of liver injury and promotes hepatocyte regeneration.

In the double-blind period of Studies BN40898 and BN40900, mild and moderate elevations of liver transaminases have been observed with satralizumab treatment. Most elevations were $<5\times$ upper limit of normal (ULN) and resolved while on treatment with satralizumab. Elevations of ALT or AST $>3\times$ ULN were not associated with increases in TBL.

Liver function markers should be closely monitored especially when satralizumab is administered, concomitantly with hepatotoxic drugs, or administered in patients with elevated transaminases.

Recommended dose interruptions based on transaminases are shown in [Table 1](#).

Table 1 Hepatic Enzyme Risk Mitigation

AST or ALT values	Action
>1 to 3× ULN ^a	
 Reduction (if necessary, interruption) of concomitant hepatotoxic drugs could be considered. For persistent increases in this range, satralizumab could be interrupted until AST and ALT is below ULN ^a.
>3 to 5× ULN	
Laboratory tests (ALT, AST, ALP and TBL) should be repeated within 72 hours to confirm value. The presence of clinical symptoms should be queried. Patients who are far away from the trial site may be retested locally if prompt return to the trial site is difficult
 
Satralizumab should be interrupted until AST and ALT is below 3× ULN. If at least one of following associated, satralizumab should be discontinued:
 
 TBL >2× ULN and/or INR >1.5× ULN and/or Appearance of fatigue, nausea, vomiting, right upper quadrant pain or tenderness, fever, rash, and/or eosinophilia
>5× ULN	
Laboratory tests (ALT, AST, ALP, and TBL) should be repeated within 72 hours. If value is confirmed, satralizumab should be discontinued immediately and gastroenterology expert should be contacted.
 
The presence of clinical symptoms should be queried. If prompt return to the trial site is difficult the patients may be retested locally.

ALP=alkaline phosphatase; ALT=alanine aminotransferase; AST=aspartate aminotransferase; INR=international normalized ratio; TBL=total bilirubin; ULN=upper limit of normal.

^a ULN or patient's baseline value in the parent study, whichever is higher.

